### **9.9. Definition of End of Study**

The end of study will be the date of last data analysis that will approximately be 3-5 days after the AF ablation of the last patient.

Subject: Research protocol	Short Title: INSIDE PVs study	Chief Investigator: [name]
		Ethics Ref:
Version/Date: 1.0 /30 th June 2016	IRAS Ref: 156673	16/WM/0379
Page 18 of 29		

## 10. INTERVENTIONS

### 10.1. CT imaging

All cardiac computed tomographic (CT) studies will be performed using an Aquilion One scanner (Toshiba Medical Systems, Otawara, Japan), with 320 detector rows (each 0.5mm wide) and a gantry rotation time of 350ms. This allows the entire heart to be imaged in a single heartbeat, from carina to diaphragm, with a maximum of 16cm crano-caudal coverage. The electrocardiogram (ECG) will be monitored to allow prospective gating of image acquisition, with a phase window set to 30-80% of the R-R interval to allow assessment of left atrial wall thickness in both atrial diastole and systole. If necessary, metoprolol will be administered intravenously in a series of doses (to a maximum of 80mg) to achieve a heart rate of 60bpm. The lowest tube voltage (100kVp or 120kVp) will be used that delivers a small focal spot based on scout image attenuation, with automatic selection of tube current (200-500mA).

A power injection of intravenous iodinated contrast (Niopam 370, or equivalent) will be given via an intravenous cannula sited in an antecubital vein. A volume of 40-80ml will be used at an infusion rate of 4-6ml/s, depending on patient morphology. This will be followed by 50ml of normal saline given at a similar rate. A region of interest will be positioned within the descending aorta on a test slice, and when the Hounsfield units exceed 180 a breath-hold and image acquisition after a 3s delay will be triggered. Given uncertainty about the optimal way to image and measure the left atrial myocardium, after a delay of 40s, a second (“venous phase”) acquisition will be performed using the same parameters as the first.

Images will be reconstructed iteratively with soft and sharp kernels, with a slice thickness of 0.5mm and an increment of 0.25mm. Analysis will be performed on a dedicated post-processing workstation (Terarecon). The thickness of the left atrial wall will be measured at a number of locations and especially in correspondence of the circumferential ablation line, identified retrospectively by using PV branching as anatomical markers. Of note, measurements will be optimally standardized according to position, phase of the R-R interval and arterial versus venous acquisition as this is another important aim of this pilot study.

Based on previous experience with an Aquilion One scanner ([name]), a prospectively gated scan covering 30-80% of the R-R interval (9 patients, range of kVp) delivers a dose-length-product of  $165 \pm 100$  mGy.cm. Therefore, the total DLP for study patients having two acquisitions (arterial and venous) before ablation and two afterwards will be 660 mGy.cm. Using a conversion factor of 0.014 mSv/mGy.cm, this equates to a mean effective dose equivalent of 9mSv.

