**Ethics Ref:**

16/WM/0379

**Version/Date:** 1.0 /30th June 2016    **IRAS Ref:** 156673

Secondary Objectives	Secondary Outcome Measure	
1. Feasibility of ICE/IVUS for real time imaging of the LA thickness and PV ostial diameters during AF ablation	1a. Additional procedural time 1b. Image quality	Day of AF ablation procedure
2. Comparison between acute tissue changes produced by RF, cryo and laser energy	2. Percentage change of LA wall thickness with each ablation modality (RF, cryo and laser energy)	Day of AF ablation procedure
3. Standardization of CT for LA wall thickness imaging with identification of a minimum dataset of acquisitions and reduction of radiation exposure	3. CT acquisitions associated to reproducible measurement of LA wall thickness with the lowest radiation exposure	Some days before and day after AF ablation procedure

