### **8.2. Inclusion Criteria**

The participant must satisfy the following conditions:

- Males older than 40 years or females older than 40 and sterile or in post-menopausal age;
- willing and able to give informed consent for participation in the study;
- history of symptomatic and drug-refractory paroxysmal atrial fibrillation;
- planned AF ablation on a clinical basis.

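### At the 60 bpm target, the 30-80% R-R window for CT closes at or before the expected start of atrial contraction, so section 10.1 should not claim without qualification that it allows assessment in atrial systole

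*Combined protocol and SAP*

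**What the plan says.** Section 10.1 (CT imaging) specifies prospective ECG gating with a "phase window set to 30-80% of the R-R interval to allow assessment of left atrial wall thickness in both atrial diastole and systole". Rate control is given if necessary "to achieve a heart rate of 60bpm". The scanner has a "gantry rotation time of 350ms". The dose estimate that closes section 10.1 rests on "a prospectively gated scan covering 30-80% of the R-R interval", so the window is deliberate and not a typing slip.

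Phase is meant to be used in the analysis. The same section says that "measurements will be optimally standardized according to position, phase of the R-R interval and arterial versus venous acquisition", and presents this as an important aim of the pilot. It serves secondary outcome 3 in section 6, the "CT acquisitions associated to reproducible measurement of LA wall thickness with the lowest radiation exposure".

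The protocol does not say where atrial systole falls in the R-R interval. It gives no PR interval, and it does not say whether 80% is the end of exposure or the centre of the last reconstruction. Participants have a "history of symptomatic and drug-refractory paroxysmal atrial fibrillation" (section 8.2), but no rhythm is required at the scan.

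**The concern.** Atrial contraction follows the P wave and comes before the next ventricular activation, so in sinus rhythm it belongs to the last part of the R-R interval. A window that stops at 80% leaves that part out. The window is thus justified by a property that it does not appear to have.

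What is at stake is the phase part of secondary objective 3. If the late images in the window are read as atrial systole, a comparison of systole with diastole would rest on images from another phase. The pilot could then recommend or discard atrial systole for the reduced CT dataset without having properly imaged it, and a later CT protocol could inherit the error.

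**Working it through.** The plan gives no timing figure to reproduce. The only figure tied to the window is the dose: 4 acquisitions x 165 = 660 mGy.cm, and 660 x 0.014 = 9.24 mSv. This agrees with the stated 660 and 9, but does not bear on timing.

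**Inputs from section 10.1.** Window 30-80% of R-R; target rate 60 bpm; gantry rotation 350 ms.

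**Assumed inputs, not in the documents.** PR 120-200 ms; Q, the time from QRS onset to R peak, 0-40 ms; D, the delay from P wave to mechanical contraction, 50-100 ms, with 0 as a limiting case.

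**Step 1: the window.** R-R = 60000 / 60 = 1000 ms. The window runs from 0.30 x 1000 = 300 ms to 0.80 x 1000 = 800 ms. The omitted end is 1000 - 800 = 200 ms.

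**Step 2: onset of contraction at 60 bpm.** Onset = (R-R - Q - PR + D) / R-R.

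| D (ms) | PR 120, Q 0 | PR 120, Q 40 | PR 200, Q 0 | PR 200, Q 40 |
|---|---|---|---|---|
| 0 | 88% | 84% | 80% | 76% |
| 50 | 93% | 89% | 85% | 81% |
| 100 | 98% | 94% | 90% | 86% |

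With D of 50-100 ms, onset is at 81-98%, outside the window in every combination. The narrowest margin is 10 ms (onset at 810 ms). With D = 0, onset is at 76-88%, and the most that falls inside is 800 - 760 = 40 ms.

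**Step 3: long PR at 60 bpm.** Onset before 800 ms needs PR > 200 - Q + D. For D = 50 the threshold is 210 ms (Q 40) to 250 ms (Q 0). For D = 100 it is 260 to 300 ms. As an example, PR 240, Q 40 and D 50 give onset at 1000 - 40 - 240 + 50 = 770 ms (77%), so 30 ms is inside.

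**Step 4: faster rates.** The time inside the window is (PR + Q - D) - 0.20 x R-R, when positive.

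- 75 bpm (R-R 800 ms), PR 200, D 50-100: onset at 76-88%. The largest overlap is (200 + 40 - 50) - 160 = 30 ms.
- 90 bpm (R-R 667 ms), PR 200, D 50-100: onset at 71.5-85%. The largest overlap is 190 - 133 = 57 ms.

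In these two largest-overlap cases contraction starts 190 ms before the next R wave, so most of the time from onset to R is still missed.

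**Step 5: if 80% is a reconstruction centre.** Assuming half-rotation reconstruction, each image uses 350 / 2 = 175 ms of data. Centred on 800 ms, that spans 712.5 to 887.5 ms. Such an image may include early contraction, mixed with the period before it.

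**The case against.** The strongest objection is that the conflict rests on physiology outside the documents. PR, mechanical delay, scan rhythm and the meaning of 80% are all unstated, and 60 bpm is a target that not every scan need meet. That stands. A reader might infer that the window cannot capture any atrial systole. The documents do not support this, because steps 2 to 5 show ways in which part of early contraction could be included. Those routes yield a fragment or a blend of phases, however, which does not support the unqualified claim in section 10.1.

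The second objection is that the harm is inferred. Secondary outcome 3 never names atrial systole. Elsewhere the protocol uses acquisitions for the arterial and venous contrast passes, and results labelled by percentage of R-R would be correct whatever the physiological label. This also stands: a reader might infer that the study is committed to reporting an atrial-systole measurement, and no such output is planned. But section 10.1 names atrial systole as a reason for the window and makes R-R phase a factor in standardisation, so mislabelling is a real possibility. If ventricular or atrial filling phases were meant, the sentence would still need correcting.

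A third tempting argument is that a patient scanned in AF has no organised atrial systole. That would be true of any window, so it is no evidence against this one. It is only a reason to record the rhythm.

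**Conclusion.** The point holds as a mismatch between the stated purpose and the stated window. At 60 bpm the window omits the last 200 ms of the cycle. Under the assumed sinus-rhythm timings with a 50-100 ms mechanical delay, contraction begins after the window closes. In the limiting case of no delay, at most about 40 ms is inside. The window does not reliably cover atrial systole, and section 10.1 should not say without qualification that it does.

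The consequence is limited to the diastole/systole wording and to the phase part of secondary objective 3. Nothing shows that the primary comparison of CT with ultrasound is affected, since it can use the images within the window. The conclusion depends on the assumed PR, Q and D ranges and on sinus rhythm near the target rate.

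**What to change.** - In section 10.1, reconcile the stated purpose with the window: remove the unqualified claim to assess atrial systole, and state whether 80% is the end of exposure or the centre of the last reconstruction.
- Report phase results by percentage of R-R, with the rhythm and heart rate at each scan.
- Limit any phase conclusion under secondary objective 3 to the phases actually acquired, and draw none about atrial systole.
- If the sponsor needs atrial systole, the window, the claim and the dose estimate in section 10.1 must be reconciled together, because that estimate is based on a 30-80% scan. No particular window is proposed here.

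The first three changes cost wording and two recorded items per scan (rhythm and rate), with no added scan or radiation. The price is a slightly narrower claim about phase.

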### 10.2. Intra-procedural ultrasound imaging (ICE/IVUS)

Ultrasound imaging via ICE or IVUS will be performed in each patient during the AF ablation procedure. IVUS catheters Visions PV .018 (20 MHz digital probe, maximum imaging diameter 24 mm, Volcano Corp) or

Subject: Research protocol	Short Title: INSIDE PVs study	Chief Investigator: [name]
Ethics Ref:		
Version/Date: 1.0 /30 th June 2016	IRAS Ref: 156673	16/WM/0379
Page 19 of 29		

ICE catheters Ultra ICE (9 MHz rotational transducer, maximal radial depth 50 mm, Boston Scientific) will be alternatively used. Before RF/cryo/laser delivery for PVI, the imaging catheter will be introduced in the LA. It will be sequentially placed in each PV, 1-2 cm distal to the ostium. Images will be recorded during slow retraction of the probe with a motorized linear pullback system from each vein to the trans-septal access. The same process will be repeated after PVI.

Reproducibility will be assessed by repeating the image acquisition via motorized linear pullback at least twice before and twice after PVI in two randomly chosen veins per patient.

## **11. SAFETY REPORTING**

### **11.1. Definition of Serious Adverse Events**

A serious adverse event is any untoward medical occurrence that:

- results in death
- is life-threatening
- requires inpatient hospitalisation or prolongation of existing hospitalisation
- congenital anomaly/birth defect
- results in persistent or significant disability/incapacity

Other 'important medical events' may also be considered serious if they jeopardise the participant or require an intervention to prevent one of the above consequences.

NOTE: The term "life-threatening" in the definition of "serious" refers to an event in which the participant was at risk of death at the time of the event; it does not refer to an event which hypothetically might have caused death if it were more severe.

### **11.2. Reporting Procedures for Serious Adverse Events**

A serious adverse event (SAE) occurring to a participant should be reported to the REC that gave a favourable opinion of the study where in the opinion of the Chief Investigator the event was 'related' (resulted from administration of any of the research procedures) and 'unexpected' in relation to those procedures. Reports of related and unexpected SAEs should be submitted within 15 working days of the Chief Investigator becoming aware of the event, using the HRA report of serious adverse event form (see HRA website).

## **12. STATISTICS AND ANALYSIS**

Subject: Research protocol	Short Title: INSIDE PVs study	Chief Investigator: [name]
		Ethics Ref:
Version/Date: 1.0 /30 th June 2016	IRAS Ref: 156673	16/WM/0379
Page 20 of 29		

### **12.1. The Number of Participants**

This investigational study aims at building a model for real-time imaging of LA wall thickness and acute changes produced by catheter ablation for AF. As pilot study, it will enrol 12 patients elected to AF ablation with radiofrequency energy (4 patients), cryo-balloon (4 patients) or laser balloon (4 patients).

As each patient will undergo two cardiac CT scans (one before and after AF ablation), with LA wall thickness measurements in different locations, and repeated intra-procedural ultrasound imaging, with 1-2 acquisitions before and 1-2 acquisitions shortly after RF delivery for PVI in each PV, we expect that at the end of the study we will have enough information to confirm if intra-procedural ICE and/or IVUS are feasible for real-time imaging of the LA wall thickness during AF ablation and to streamline the CT protocol to a minimum dataset of acquisitions, with reduced radiation exposure. The study could also give us some insights about different mechanisms of lesion formation and different acute tissue changes caused by the different energy modalities, to be investigated further in a bigger randomized study.

### **12.2. Description of Statistical Methods**

Comparison of primary, secondary and tertiary outcome measures among different treatment groups will be performed at each time point using appropriate statistical testing. In particular, ANOVA tests will be used to compare numerical variables and chi-square tests will be used to compare categorical values.

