#### 4.3 Research questions

- Intra-procedural ultrasound techniques (ICE and IVUS) have not previously been evaluated for LA wall imaging (thickness and acute changes in response to ablation) during PV isolation ablation.  
**How feasible is it to use these technologies for this purpose and do they provide accurate and reliable measurements compared to the gold standard of cardiac CT?**
- **Are there any differences in terms of acute tissue changes produced by the different energy modalities for AF ablation?**
- **What is the minimum dataset of CT acquisitions for a reproducible measurement of LA wall thickness with the lowest radiation exposure?**

Subject: Research protocol	Short Title: INSIDE PVs study	Chief Investigator: [name]
Ethics Ref:		
Version/Date: 1.0 /30 th June 2016		16/WM/0379
Page 9 of 29		

We plan to address these questions in order to build a user-friendly, reliable and safe model to image the LA wall and to measure the acute tissue changes occurring during catheter ablation for AF.

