## 5. STUDY DESIGN

Patients scheduled for their first pulmonary vein isolation ablation for symptomatic, drug-refractory paroxysmal AF, will be considered for inclusion in the study.

Potential subjects will initially be approached some weeks before their ablation procedure, in order to give the patients enough time to consider the information, to ask questions to the Investigator, their general practitioner (GP) or other independent parties to decide whether they wish to participate in the study or not.

For those interested in participation, a baseline assessment will be arranged to coincide with their standard pre-admission visit, for informed consent, screening and eligibility assessment. Moreover, a pre-operative imaging assessment with a cardiac CT scan will be performed to define the LA and PV anatomy and to measure the baseline LA wall thickness and PVs ostial diameters.

All AF ablation procedures will be performed in a standard fashion by using RF energy, cryo-balloon or laser balloon ablation under general anaesthesia (5) and with continuous oesophageal temperature monitoring. Ultrasound imaging by IVUS or ICE will be performed at sites corresponding with the PV/LA junction at the beginning and the end of the procedure in order to measure acute changes in LA wall thickness and PV ostial diameters.

The cardiac CT will be repeated within 24 hours post-procedure.

After the procedure, a pre-discharge review and a telephone follow-up at 1 week will be performed to identify any early and late complications related to the procedure.

A total of 12 patients will finally be enrolled in the study, 4 for each energy modality (RF, cryo and laser).

The end of the study for each patient will be the date of the telephone follow-up 1 week after the procedure.

For each patient the pre-procedural and post-procedural CT measurements of LA wall thickness and PVs ostial diameters will be compared with the corresponding IVUS or ICE measurements. Moreover, the acute tissue changes produced by the different energy modalities will be compared. Table 1 shows the main differences between the standard NHS process for AF ablation and the INSIDE PVs study appointments.

Standard NHS process for AF ablations	INSIDE PVs study appointments
Referral for procedure	Identification of participants

Subject: Research protocol	Short Title: INSIDE PVs study	Chief Investigator: [name]
Ethics Ref: 16/WM/0379		

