## 6. OBJECTIVES AND OUTCOME MEASURES

Objectives	Outcome Measures	Timepoint(s) of evaluation of this outcome measure (if applicable)
Primary Objective  1. Evaluation of the accuracy of intra-procedural intracardiac echocardiography (ICE) and intravascular ultrasound (IVUS) for real time imaging of the LA wall thickness and PV ostial diameters during AF ablation	Primary Outcome Measure  1. ICE/IVUS measurements of LA wall thickness and PV ostial diameters before and after pulmonary vein isolation (PVI) in comparison with the corresponding cardiac CT measurements (before and the day following the AF procedure)	1. Day of and day after AF ablation procedure

**Subject:** Research protocol

**Short Title:** INSIDE PVs study

**Chief Investigator:** [name]

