### **9.7. Image integration and data analysis**

The pre-procedural CT images and the post-procedural CT images will be compared for each patient.

Moreover, the pre and post-procedural CT images will be compared with the corresponding IVUS or ICE images. The plane of the circumferential ablation line will be identified by using PV branching as reference anatomical markers and it will be divided into 12 segments by using a clock-face model. The LA wall thickness will be measured at each segment and comparisons will be made between pre and post-ablation and between IVUS/ICE and CT at each timepoint.

The percentage changes in LA wall thickness after AF ablation will be compared between the three energy modalities (RF, cryo and laser).

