### **12.3. Analysis of Outcome Measures**

Summary statistics, including means, medians, and variances, will be calculated at each time point and for each type of data (e.g. parameters derived from index AF procedure and follow-up visits).

If patients withdraw from the study we will analyse data already collected, unless the patients request otherwise. For every participant who withdraws, another participant will be sought in order to have a total of 12 full datasets for 12 participants.

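### The primary accuracy comparison of ICE/IVUS with CT has no agreement statistic: the only test named for it is ANOVA among treatment groups, which cannot see a bias shared by the groups

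*Combined protocol and SAP*

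**What the plan says.** Section 4.3 asks of ICE and IVUS: "do they provide accurate and reliable measurements compared to the gold standard of cardiac CT". Section 6 turns this into the primary outcome, the ultrasound "measurements of LA wall thickness and PV ostial diameters before and after pulmonary vein isolation (PVI) in comparison with the corresponding cardiac CT measurements".

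The matched comparison is planned. Section 5 says the CT measurements "will be compared with the corresponding IVUS or ICE measurements". Section 9.7 takes the plane of the circumferential ablation line and says "it will be divided into 12 segments by using a clock-face model", after which "comparisons will be made between pre and post-ablation and between IVUS/ICE and CT at each timepoint". Neither section names a statistic or model.

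The statistical section is short. Section 12.2 reads: "Comparison of primary, secondary and tertiary outcome measures among different treatment groups will be performed at each time point using appropriate statistical testing". It continues that "ANOVA tests will be used to compare numerical variables and chi-square tests will be used to compare categorical values". Section 12.3 adds: "Summary statistics, including means, medians, and variances, will be calculated at each time point and for each type of data". Section 10.2 plans repeat pullbacks to assess ultrasound reproducibility, again without a statistic.

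Nowhere does the supplied text name a paired difference, limits of agreement, an intraclass or concordance correlation, a paired test or an acceptable difference.

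**The concern.** Accuracy against a reference is a question about paired differences: how far ultrasound lies from CT on average, and how widely it scatters around CT at a given site. Section 12.2 explicitly includes the primary outcome, but the contrast it describes is between RF, cryo and laser patients. If the ANOVA is run on ultrasound values alone, CT does not enter. If it is run on the ultrasound-minus-CT differences, a bias shared by the three groups drops out of the F statistic.

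At stake is the main result of the study. The matched data will exist, partly through a post-ablation CT that Section 7 describes as outside standard care, yet the plan does not say how they become a statement about accuracy. Leaving the method open until the data are seen also invites a naive one, such as treating the many segments within a patient as independent.

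**Working it through.** **Inputs from the documents.** 12 patients, 4 per energy modality (Sections 5 and 12.1); 12 segments per ablation line (9.7); ICE or IVUS in each patient, split not given (10.2). The plan states no alpha, SD, correlation, margin or precision target, so it has no figure to reproduce. Correlations, ICCs and segments per patient below are assumptions, shown over a range.

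**1. Shared bias and the among-group ANOVA.** Take illustrative differences {0.1, 0.5, −0.2, 0.3}, {0.6, 0.2, 0.9, 0.4}, {−0.1, 0.3, 0, 0.5}. Group means are 0.175, 0.525 and 0.175. The between-group mean square is 0.3267/2 = 0.1633, the within-group mean square is 0.7625/9 = 0.0847, and F = 1.928 (p = 0.20). Adding 0, 1, 2 or 10 to every difference leaves F at 1.928, while the mean difference is 0.29, 1.29, 2.29 or 10.29. In 5,000 simulated studies per setting, with biases of 0, 1, 2 and 5 SD, the group F test rejected in 4.7%, 4.1%, 4.7% and 5.1%. A one-sample test on the same differences rejected in 4.8%, 88.1%, 100% and 100%.

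**2. What the Section 12.3 summaries can give.** With complete pairs, mean(ultrasound) − mean(CT) equals the mean paired difference, so a crude bias estimate can be derived. Its standard error and the limits of agreement need the variance of the differences, and so the ultrasound–CT covariance, which separate means, medians and variances do not contain. Two cases, at correlation ρ:

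| ρ (assumed) | Equal means and variances: limits, 1.96·√(2(1−ρ)), in SD of one method | Ultrasound = CT + independent error: limits, 1.96·√(1/ρ²−1), in CT SD | Ultrasound/CT variance ratio in the second case, 1/ρ² |
|---|---|---|---|
| 0.95 | ±0.62 | ±0.64 | 1.11 |
| 0.9 | ±0.88 | ±0.95 | 1.23 |
| 0.5 | ±1.96 | ±3.39 | 4.0 |

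In the first case, a worst case, the 12.3 output is identical in all three rows. In the second, the variances would reveal gross scatter but show moderate scatter only faintly.

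**3. Could another ANOVA supply it?** With site and imaging method as factors, the residual mean square equals half the variance of the differences (48 simulated sites: 0.10675 both ways). Limits could be built from that residual, or from the error term of a one-way ANOVA on the differences. Section 12.2 plans neither model for this purpose, nor the reporting of that quantity.

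**4. Precision after the fix, one value per patient.** With n = 12 and t(11) = 2.201, in SD of the patient-level differences:
- bias: 2.201/√12 = 0.64
- each limit: 2.201·√(1/12 + 1.96²/22) = 1.12

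For 6 patients on one device (an assumed even split) the same formulas give 1.05 and 1.91.

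**5. Precision at segment level.** Section 9.7 does not give the number of lines per patient; 2 or 4 lines would mean k = 24 or 48 segments. With total SD 1, the bias half-width is 2.201·√((ICC + (1−ICC)/k)/12). The half-width for a limit is 2.201 times the simulated SD of the variance-component limit (200,000 runs). The last column is the actual coverage of a nominal 95% interval for the bias if segments are treated as independent.

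| k | ICC | Bias ± | Each limit ± | Coverage if clustering is ignored |
|---|---|---|---|---|
| 24 | 0.05 | 0.19 | 0.27 | 82% |
| 24 | 0.1 | 0.24 | 0.31 | 72% |
| 24 | 0.3 | 0.36 | 0.49 | 51% |
| 24 | 0.5 | 0.46 | 0.66 | 41% |
| 48 | 0.05 | 0.17 | 0.22 | 71% |
| 48 | 0.1 | 0.22 | 0.27 | 59% |
| 48 | 0.3 | 0.36 | 0.46 | 38% |
| 48 | 0.5 | 0.45 | 0.65 | 30% |

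**The case against.** The best defence is that this is a 12-patient pilot with no hypothesis or margin, and that the segment-by-segment comparison is planned in Section 9.7. The wording in 12.2 about appropriate testing is open, so ANOVA and chi-square may be examples rather than the full list. Nothing collected would change, and the method could be settled at any time before analysis.

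Part of this stands. A reader might infer that no ultrasound–CT comparison is planned, or that the sponsor means to judge accuracy by a between-energy F test. Sections 5 and 9.7 do not support that: the comparison is there, and what is missing is its method. A reader might also infer that the primary question would have no estimate at all. That goes too far, because the 12.3 means yield a crude bias when ultrasound and CT are summarised separately over the same complete pairs. Nor is ANOVA incapable in principle, as step 3 shows.

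The rest does not stand. The open wording in 12.2 is tied to comparison among treatment groups, and no imaging-method factor or pairing is mentioned. Pilot status explains the absence of a power calculation; it does not supply an analysis for the stated primary objective.

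A fair practical objection is that ultrasound minus CT is not yet a defined quantity. Section 10.1 produces arterial and venous acquisitions over 30–80% of the R-R interval with two kernels, and choosing among acquisitions is secondary objective 3. Section 12.1 allows 1–2 ultrasound acquisitions per vein before and after ablation. The fix must settle this.

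**Conclusion.** The concern holds in this form: a matched comparison is planned without a statistic, and the one inferential method named for the numerical primary outcome cannot detect or estimate a bias common to the energy groups. The plan offers at most a crude point estimate of bias, without precision, paired scatter or limits of agreement.

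The invariance of F to a shared bias is algebraic and rests on no assumption; the 12 differences only illustrate it. How much scatter the 12.3 summaries could hide depends on the assumed correlation and on whether the two methods have equal variances. The segment-level precision and coverage figures depend on the assumed ICC and segment count. None of these figures predicts what this study will find.

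**What to change.** In Sections 12.2 and 12.3:

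- **Primary analysis.** Ultrasound minus CT at each matched segment (wall thickness) or vein (ostial diameter). Report mean bias with 95% CI and 95% Bland-Altman limits of agreement with CIs, with patient as the cluster.
- **Definition of the pair.** Before the comparison is made, fix one CT reference (acquisition, R-R phase, kernel) and the ultrasound pullback, or mean of pullbacks, to be used. Treat the other CT acquisitions as sensitivity analyses.
- **Strata.** Report by device (ICE, IVUS), descriptively if few patients had that device. Report pre-PVI and post-PVI pairs separately, both kept as primary as in Section 6.
- **Interpretation.** CT and ultrasound are not simultaneous: the first CT is 1–2 weeks before ablation (9.1) and the second within 24 h after it (9.5). Describe post-PVI differences as measurement difference plus possible real tissue change, not as pure bias.
- **Repeatability.** Report it from the repeat pullbacks in 10.2.
- **Status.** State that the pilot estimates agreement, unless an acceptable difference is set beforehand.
- **ANOVA.** Keep the between-energy ANOVA for secondary objective 2, as exploratory.

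The cost is wording, modest analysis and an early decision on the CT reference, which touches secondary objective 3. No new patients, scans or staff are needed. The downside is that the estimates will be visibly imprecise, more so by device.
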